8.10. Other aspects

Not applicable

9. PROTECTION OF HUMAN SUBJECTS

9.1. Patient information

All parties will comply with all applicable laws, including laws regarding the implementation of organizational and technical measures to ensure protection of patient personal data. Such measures will include omitting patient names or other directly identifiable data in any reports, publications, or other disclosures, except where required by applicable laws.

Patient personal data will be stored at Maccabi Research & Innovation Institute in encrypted electronic and/or paper form and will be password protected or secured in a locked room to ensure that only authorized study staff have access. MHS will implement appropriate technical and organizational measures to ensure that the personal data can be recovered in the event of disaster. In the event of a potential personal data breach, MHS shall be responsible for determining whether a personal data breach has in fact occurred and, if so, providing breach notifications as required by law.

To protect the rights and freedoms of natural persons with regard to the processing of personal data, when study data are compiled for transfer to Pfizer and other authorized parties, any patient names will be removed and will be replaced by a single, specific, numerical code. All other identifiable data transferred to Pfizer or other authorized parties will be identified by this single, patient-specific code. In case of data transfer, Pfizer will maintain high standards of confidentiality and protection of patients' personal data consistent with the research agreement and applicable privacy laws.

9.2. Patient consent

As this study does not involve data subject to privacy laws according to applicable legal requirements, obtaining informed consent from patients by Pfizer is not required and exemption will be received from the ethics committee.

9.3. Institutional review board (IRB)/Independent ethics committee (IEC)

There must be prospective approval of the study protocol, protocol amendments, and other relevant documents (e.g., informed consent forms if applicable) from the relevant IRBs/IECs. The study will be conducted per approval of the Maccabi Research Committee and the local Institutional Review Boards.

All correspondence with the IRB/IEC must be retained. Copies of IRB/IEC approvals must be forwarded to Pfizer.

9.4. Ethical conduct of the study

The study will be conducted in accordance with legal and regulatory requirements, as well as with scientific purpose, value and rigor and follow generally accepted research practices described in:

- Good Practices for Outcomes Research issued by the International Society for Pharmacoeconomics and Outcomes Research (ISPOR)
http://www.ispor.org/workpaper/practices_index.asp
- International Ethical Guidelines for Epidemiological Studies issued by the Council for International Organizations of Medical Sciences (CIOMS)
- Food and Drug Administration (FDA) Guidance for Industry: Good Pharmacovigilance Practices and Pharmacoepidemiologic Assessment
- Israeli Ministry of Health regulation 14 – Medical trials in Human subjects

10. MANAGEMENT AND REPORTING OF ADVERSE EVENTS/ADVERSE REACTIONS

This study protocol requires human review of patient-level unstructured data; unstructured data refer to verbatim medical data, including text-based descriptions and visual depictions of medical information, such as medical records, images of physician notes, neurological scans, x-rays, or narrative fields in a database. The reviewer is obligated to report adverse events (AEs) with explicit attribution to any Pfizer drug that appear in the reviewed information (defined per the patient population and study period specified in the protocol). Explicit attribution is not inferred by a temporal relationship between drug administration and an AE but must be based on a definite statement of causality by a healthcare provider linking drug administration to the AE.

The requirements for reporting safety events on the non-interventional study (NIS) adverse event monitoring (AEM) Report Form to Pfizer Safety are as follows:

- All serious and non-serious AEs with explicit attribution to **any Pfizer drug** that appear in the reviewed information must be recorded on the data collection tool and reported, within 24 hours of awareness, to Pfizer Safety using the NIS AEM Report Form.
- Scenarios involving drug exposure, including exposure during pregnancy, exposure during breast feeding, medication error, overdose, misuse, extravasation, lack of efficacy, and occupational exposure associated with the use of a Pfizer product must be reported, within 24 hours of awareness, to Pfizer Safety using the NIS AEM Report Form.

- For these AEs with an explicit attribution or scenarios involving exposure to a Pfizer product, the safety information identified in the unstructured data reviewed is captured in the Event Narrative section of the report form, and constitutes all clinical information known regarding these AEs. No follow-up on related AEs will be conducted.

All the demographic fields on the NIS AEM Report Form may not necessarily be completed, as the form designates, since not all elements will be available due to privacy concerns with the use of secondary data sources. While not all demographic fields will be completed, at the very least, at least one patient identifier (e.g., gender, age as captured in the narrative field of the form) will be reported on the NIS AEM Report Form, thus allowing the report to be considered a valid one in accordance with pharmacovigilance legislation. All identifiers will be limited to generalities, such as the statement “A 35-year-old female...” or “An elderly male...” Other identifiers will have been removed.

Additionally, the onset/start dates and stop dates for “Illness,” “Study Drug,” and “Drug Name” may be documented in month/year (mmm/yyyy) format rather than identifying the actual date of occurrence within the month /year of occurrence in the day/month/year (DD/MMM/YYYY) format.

All research staff members must complete the following Pfizer training requirements:

- “*Your Reporting Responsibilities (YRR) Training for Vendors.*”

These trainings must be completed by research staff members prior to the start of data collection. All trainings include a “Confirmation of Training Certificate” (for signature by the trainee) as a record of completion of the training, which must be kept in a retrievable format. Copies of all signed training certificates must be provided to Pfizer.

Human Review of Structured Data

This study involves data that exist as structured data by the time of study start. In these data sources, individual patient data are not retrieved or validated, and it is not possible to link (i.e., identify a potential association between) a particular product and medical event for any individual. Thus, the minimum criteria for reporting an adverse event (AE) (i.e., identifiable patient, identifiable reporter, a suspect product, and event) cannot be met.

11. PLANS FOR DISSEMINATING AND COMMUNICATING STUDY RESULTS

A report will be provided on completion of the entire study in a Word format. This report will incorporate methodology, sample, tables of results and summaries. All documents used throughout the study will be contained within the report as appendices. Results of this study may be submitted to conferences and journals for publication. As per Pfizer’s requirements, the project will only be considered complete upon delivery of the full study report and close of all study publications.

In the event of any prohibition or restriction imposed (e.g., clinical hold) by an applicable competent authority in any area of the world, or if MHS is aware of any new information which might influence the evaluation of the benefits and risks of a Pfizer product, Pfizer should be informed immediately.

ANNEX 1. LIST OF STAND ALONE DOCUMENTS

1. Baseline demographic and clinical characteristics of patients diagnosed with metastatic breast cancer 2018-2019 split by Palbociclib as first-, second- or third line (n=XX).

		First Line	Second Line	Third Line	Total n=XXX

Demographic Variables					
Age	median (IQR)				
	<65				
	≥65				
Gender	male				
	female				
Region of residence	Central				
	North				
	South				
Socioeconomic status*	low				
	medium				
	high				
Clinical Variables					
Deyo-Charlson Comorbidity Index (without malignancy or HIV)	mean (SD)				
	0				
	1				
	2				
	3				
	≥4				
Co-morbidities	Diabetes mellitus				
	Cardiovascular disease				
	Stroke				
	Congestive heart failure				
	Hypertension				
	Chronic kidney disease				

	Chronic obstructive pulmonary disease			
	Other (e.g. depression)			
Co-medications				
Smoking	Ever smoker			
	Never smoker			
	Unknown			
BMI				
Menopausal status	Pre/Peri menopausal			
	Postmenopausal			
Genetic counselling for gBRCAm	Yes			
	No			
Testing for gBRCAm	Yes			
	No			

2. Cancer related characteristics of patients with breast cancer at baseline

		First Line	Second Line	Third Line	Total (n)
Histology					
Location of metastases	Brain				
	Bone				

	Visceral				
	Lymph nodes				
	Other				
ECOG	0-1				
	2				
	3-4				
	Unknown/missing				
Hormone sensitivity	Primary				
	Secondary				
Molecular status data: performed HER2 / HR tests	HR+ [Estrogen Receptor positive (ER+), Progesterone Receptor positive (PR+) or both]				
	HER2+				

3. Time on Palbociclib treatment

Line of treatment (first-, second- or third line)	N	Number (%) discontinued	Median time on treatment (95% CI), months	% on treatment at 3 months	% on treatment at 6 months	% on treatment at 12 months	% on treatment at 24 months	Log rank P value

4. Palbociclib treatment patterns

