7. RESEARCH QUESTION AND OBJECTIVES

Primary Objective: To describe patient demographics, clinical characteristics, clinical outcomes and treatment patterns of adult breast cancer patients who have initiated palbociclib combination treatment as per the national basket of health services in January 2018 until August 2020 for all lines of therapy. Extended follow up for treatment patterns to 30th June 2022.

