8. RESEARCH METHODS

8.1. Study design

This is a population based retrospective database study that will include patients with metastatic, HR+/ HER2- breast cancer and who initiated first or subsequent lines of treatment with palbociclib. Data will be available from Maccabi Healthcare Services (MHS) database in Israel for patients who received approval for treatment with palbociclib since 01 January 2018 until 31 August 2020.

Treatment amendment and extension: Treatment lines will be rerun for the same patient cohort for an additional year and a half of follow-up to 30 June 2022.

The database review followed by a medical record review will capture data from approximately 500-700 patients on demographics, clinical characteristics, disease history, treatment history, palbociclib dosing, clinical outcomes and post-palbociclib combination therapy treatment data. The study will be descriptive in nature therefore no control or comparator groups will be included.

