8.2. Setting

Patients (age \geq 18 years) will be identified from MHS purchase data between 01 July 2017 until 31 August 2020.

Index date will be defined as date of initiation of palbociclib treatment.

Patient records must meet the following criteria to be eligible for the medical record reviews. Patients must be at least 18 years of age at index date and they must have been diagnosed with HR+/HER2- ABC/ MBC. Patients must have received palbociclib combination in line with Israel approved indications. A minimum of 6 months follow up of palbociclib combination therapy prior to date of medical record review will be necessary for inclusion. This will permit the capture of meaningful clinical outcomes data. Patients will be followed through the end of the observation period, date of death or left the health maintenance organization (HMO).

A full list of the inclusion criteria can be found in Section 9.2.1.

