8.2.1. Inclusion criteria

Patients must meet all of the following inclusion criteria to be eligible for inclusion in the study:

1. A diagnosis of metastatic breast cancer, based on the National/MHS cancer registry.
2. Newly diagnosed metastatic breast cancer patients and newly treated with palbociclib within 6 months of diagnosis, in any line of treatment in the metastatic setting.
3. Available data on palbociclib treatment for at least 6 months.
4. Continuous healthcare plan enrolment in MHS for at least one year before index date.
5. At least 18 years of age at index date.

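### The year range in the Table 1 title conflicts with the cohort definition; applied literally, it would leave eligible patients out of the baseline table

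*Combined protocol and SAP*

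**What the plan says.** - **Annex 1, Table 1 shell.** The title begins "Baseline demographic and clinical characteristics of patients diagnosed with metastatic breast cancer 2018-2019". The selecting variable is the date of metastatic diagnosis and the window is two calendar years. No other text says whom Table 1 covers.
- **Section 7.** The primary objective concerns patients who started palbociclib "in January 2018 until August 2020 for all lines of therapy".
- **Section 8.1.** Data are for patients who "received approval for treatment with palbociclib since 01 January 2018 until 31 August 2020".
- **Section 8.2.** "Index date will be defined as date of initiation of palbociclib treatment". Patients "will be identified from MHS purchase data between 01 July 2017 until 31 August 2020", which opens the window six months before the date in section 8.1.
- **Section 8.2.1.** Criterion 2 takes patients "newly treated with palbociclib within 6 months of diagnosis, in any line of treatment in the metastatic setting". Criterion 3 asks for at least 6 months of palbociclib data. No criterion names a year of diagnosis.
- **Section 8.7.** Descriptive analyses are planned for the whole group and by study cohort, but no cohorts and no analysis set for any table are defined.
- **Tables 2 to 4** carry no year limit. Section 8.5 expects about 500-700 eligible patients.

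**The concern.** The shell and the methods sections select on different variables over different windows. A patient diagnosed in February 2020 who starts palbociclib in March 2020 can meet every criterion but falls outside Table 1 as titled. So does a patient diagnosed in November 2017 who starts in January 2018, the month from which section 6 dates reimbursement.

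Demographics and clinical characteristics are the first items of the primary objective, and Table 1 is where most of them are reported. It is also the table that tells a reader whose time on treatment (Table 3) and dose changes (Table 4) are being shown. A programmer who follows the shell would filter on diagnosis year; one who follows section 8 would not. The same plan could therefore yield two different baseline tables, one of which would not match the denominator of the outcome tables. Any patients lost would come from the two calendar ends of the cohort, not from a random subset.

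**Working it through.** The plan gives no figure for the share of patients in Table 1, so there is nothing to reproduce. The check is one of calendar overlap.

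**Inputs**
- Table 1 window: 1 January 2018 to 31 December 2019 = 365 + 365 = 730 days of diagnosis dates (Annex 1).
- Index window A: 1 January 2018 to 31 August 2020 = 365 + 365 + 244 = 974 days (sections 7 and 8.1).
- Index window B: 1 July 2017 to 31 August 2020 = 184 + 974 = 1158 days (section 8.2).
- Lag L from diagnosis to palbociclib start: 0 to 6 months, about 183 days at most (section 8.2.1).
- Accrual by date and the distribution of L: not given. Constant accrual is an assumption.

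**Step 1: full windows, constant accrual.** With diagnosis date = index date - L, window A gives:
- diagnosed before 2018: L/974
- diagnosed in 2020: (244 - L)/974
- total outside Table 1: 244/974 = 25%

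Under constant accrual L cancels from the total and only moves the split: 0% before 2018 and 25% in 2020 at L = 0; 19% and 6% at 6 months. For window B the total is (1158 - 730)/1158 = 428/1158 = 37%.

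**Step 2: the 6-month data rule.** The plan does not say by what date the 6 months must be complete. If the follow-up extended to 30 June 2022 counts, the rule does not shorten either window. Two stricter readings do:
- *By the implied original cut-off.* Section 8.1 adds a year and a half to reach 30 June 2022, which implies a cut-off near 31 December 2020. Index dates then end about 30 June 2020.
- *By the start of data collection*, 8 November 2020 (section 5). Index dates then end about 8 May 2020.

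| 6 months of data complete by | January 2018 start | July 2017 start |
|---|---|---|
| No shortening | 244/974 = 25% | 428/1158 = 37% |
| About 31 December 2020 | 182/912 = 20% | (1096 - 730)/1096 = 33% |
| 8 November 2020, L up to 129 days | 129/859 = 15% | (1043 - 730)/1043 = 30% |
| 8 November 2020, L = 6 months | 183/859 = 21% | (1043 - 676)/1043 = 35% |

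In the last row L exceeds the 129 days of 2020 index dates. No one is then diagnosed in 2020, and the index dates that fall inside Table 1 number 859 - 183 = 676 days.

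**Step 3: non-constant accrual, window A.** Let accrual change by a factor r per year. At L = 0 the share outside is (r^2.667 - r^1.999)/(r^2.667 - 1), where 2.667 = 974/365.25 and 1.999 = 730/365.25 years.
- r = 2: (6.350 - 3.996)/5.350 = 44%
- r = 0.5: (0.2502 - 0.1575)/(1 - 0.1575) = 11%

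Simulation (1,000,000 draws per case) with r from 0.5 to 2 and fixed lags of 0, 3 and 6 months stays within 11-44%. With L uniform over 0-6 months it gives 24-33%. Combining uneven accrual with the other windows widens the range further, from about 7% (8 November reading, January 2018 start) to 58% (window B).

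**In patients, out of 500-700:** 15% is 75-105, 25% is 125-175, 37% is 185-259. The 11% case is 55-77.

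**The case against.** The restriction appears only in the heading of an empty shell. Every operative statement points to the full cohort: the objective runs to August 2020, no criterion limits diagnosis year, section 8.7 promises overall analyses, and section 8.9 says the study aims to include all metastatic patients treated in the period. Shell titles in this annex are also loose. Table 2's title mentions neither metastatic disease nor palbociclib, yet no one would take it to admit early-stage patients. On this view the years are a label that was not updated, and no exclusion was ever planned.

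Most of that stands. A reader might infer that the plan deliberately limits Table 1 to 2018-2019 diagnoses; the documents do not support this, because no analysis text describes such a subset or filter. A reader might also infer that at least a quarter of patients would be lost. That does not hold either: 25% needs constant accrual over the whole 32 months, and a stricter reading of the 6-month rule brings it to 15-21%. The 37% depends on the July 2017 date, which conflicts with section 8.1, and on accrual before reimbursement at the same rate as after it. Nor do the documents show that age, comorbidity or other baseline features differ between the omitted patients and the rest.

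The objection does not remove the conflict. The title is the only statement of Table 1's population, and section 8.7 supplies no analysis set that would override it.

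**Conclusion.** The mismatch is certain: the Table 1 title states a population that differs from the cohort definition in both variable and dates, and nothing reconciles them. Whether any patient would actually be left out is not established, since the title may simply be out of date.

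If it is applied literally, the omitted share under constant accrual is about 15-25% with the January 2018 start. With the July 2017 start it is about 33-37% for the full window or the end-December 2020 cut-off, and 30-35% on the 8 November reading. Non-constant accrual in the 32-month window gives about 11-44%. These are conditional figures; the plan holds no accrual or lag data that would narrow them. The point deserves correction because it touches the first item of the primary objective and is easily settled before tables are produced.

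**What to change.** - Define Table 1 on all eligible patients initiating palbociclib in the study index window, with the same denominator as Tables 2 to 4, and delete the years 2018-2019 from its title.
- If a view by diagnosis year is wanted, add year of metastatic diagnosis as a row.
- Reconcile the window start dates in sections 8.1 (1 January 2018) and 8.2 (1 July 2017), since they set the common denominator.

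The cost is one title, one optional row and one date in the text, plus removal of a diagnosis-year filter if one has been programmed. No new data are needed.

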ANNEX 2. ADDITIONAL INFORMATION

Line of treatment (first-, second- or third line)	Combination partner: AI or Fulvestrant	Number (%) of dose reductions from 125mg to 100mg	Number (%) of dose reductions from 100mg to 75mg	Number (%) of dose reductions from 125mg to 75mg	Number (%) of dose Interruptions	Number (%) of discontinuations

Not applicable
